#### ***Statin adjunctive therapy for TB in mice with cell-mediated immune deficiency***

In order to determine the contribution of cellular immunity to the anti-TB effect of statins, we tested the activity of pravastatin in combination with the first-line anti-TB regimen in *Mtb*-infected athymic NU/NU (nude) mice (71).

Nude mice were aerosol-infected with *Mtb* H37Rv and treatment was initiated 4 weeks later with RHZE or RHZE + pravastatin 90 mg/kg (P90) or pravastatin 180 mg/kg (P180) administered once daily 5 days a week (5/7) for a total of 8 weeks. As expected, nude mice treated with RHZE showed significantly reduced lung CFU counts compared to the untreated control group. There is a trend toward reduced lung CFU in the RHZE+ P90 or P180 groups to RHZE alone, but this is not statistically significant (Figure 8). Thus, one may speculate the lack of bactericidal effect of statins in nude mice is probably due to deficient adaptive immunity (72), which may be required for proper activation of macrophages.

**Figure 8.** Adjunctive treatment with pravastatin (P) in *Mtb*-infected NU/NU mice.

### Potential modes of action of statins as adjunctive HDT against TB

[figure not shown]
The target enzyme of statins is HMG-CoA reductase, which catalyzes the conversion of HMG-CoA into mevalonate, a rate-limiting step in the cholesterol biosynthesis pathway (73). The mevalonate pathway is a multi-branched pathway leading to the biosynthesis of cholesterol, lipid hormones, including vitamin D, isoprenoids, and isoprenoid intermediates, such as farnesylpyrophosphate (FPP) and geranylgeranylpyrophosphate (GGPP), which are required for protein prenylation. The prenylation state of proteins, including the Rho, Rac and Ras protein families (74), results in their subcellular redistribution and membrane anchoring. In particular, Rac transduction signaling modulates generation of reactive oxygen species (ROS), which is an important mechanism by which macrophages control *Mtb* infection (75). Given the multiple functions of the mevalonate pathway, statins possess anti-inflammatory activities in addition to their well-known lipid-lowering properties. For example, statins reduce expression of pro-inflammatory chemokines and cytokines in animal models of atherosclerosis and in patients with rheumatic diseases (76-81). Indeed, the cardioprotective effect of statins is likely related to their immunomodulatory, rather than lipid-lowering, properties (74). In addition, statins appear to activate peroxisome proliferator-activated receptors (PPAR) -  $\alpha$  and - $\gamma$  in inflammatory cells and other cell types (82). PPAR- $\gamma$  regulates lipid uptake, adipogenesis, and glucose metabolism, and has been implicated in the pathology of obesity, diabetes, atherosclerosis, and cancer (83).

#### Cholesterol-lowering effect

It has been postulated that the lipid-lowering properties of statins may play a role in their anti-TB activity. *Mtb* infection induces intracellular lipid accumulation in macrophages in the form of lipid droplets (LD), quasi-organelles consisting of cholesterol esters and triglycerides surrounded by a phospholipid monolayer (84). Lipid-laden macrophages acquire a “foamy” phenotype, which is associated with

**Table 4.** Genes differentially regulated after treatment with pravastatin with and without RHZE

Treatment	Induced genes				Reduced genes			
	Fold change				Fold change			
	>10	>2	>1.5	Total	>10	>2	>1.5	Total
P30	1	37	90	128	3	18	98	119
P90	1	103	180	284	0	32	193	225
P180	1	44	190	235	0	54	223	277
RHZE	8	751	1469	2228	12	1080	1454	2546
RHZE+P90	1	235	1834	2070	4	923	1518	2445
RHZE+P180	4	678	1600	2282	19	816	1571	2406

**Figure 10.** Changes in immune cell profiles in the lungs following TB treatment and adjunctive statin therapy. RHZE plus pravastatin 90 mg/kg increased the % of lung alveolar macrophages (A), decreased TNF $\alpha$  in alveolar macrophages (B), and increased the ratio of CD4 $^{+}$ /CD8 $^{+}$  T cells in *Mtb*-infected lungs (C).  
# p<0.05 compared to no Tx (untreated). \* p<0.05 compared to RHZE.

delayed phagolysosomal maturation, enhanced IL-10 induction, alternative macrophage polarization, and blunting of innate immunity (85). Although their precise role remains poorly characterized, LD may serve as a food source for intracellular bacilli (85). In addition, their accumulation has been associated with slowed Mtb division and phenotypic tolerance to front-line drugs (55). Therefore, foamy macrophages appear to represent a stable reservoir for Mtb, facilitating persistence of the organism in the host.

[figure not shown]
We have shown that there is a correlation between the antimycobacterial and lipid-lowering activities of statins, since statin treatment of Mtb-infected macrophages reduces bacterial burden, LD formation, and intracellular cholesterol levels (17). We found that the antimicrobial effect of statins is reproduced by treatment with inhibitors of 7-dehydrocholesterol reductase (DHCR7, an enzyme required for cholesterol biosynthesis), but not with inhibitors of prenylation enzymes (FPP transferase and type I and II GGPP-transferases). However, prenylation-associated effects of statins cannot be excluded, since the inhibitory effects of statins are partially reduced by addition of GGPP (22).

In order to determine if the anti-TB activity of statins correlated with their cholesterol-lowering properties *in vivo*, we measured plasma total cholesterol and low-density lipoprotein (LDL), as well as the content of cholesterol and cholesterol esters in lung lesions using MALDI-MSI, following adjunctive therapy of Mtb-infected mice with simvastatin 60 mg/kg. No significant differences were observed between the control group and simvastatin arm with respect to cholesterol levels in plasma or lung lesions (data not shown). These results suggest that cholesterol depletion is unlikely to be the major mechanism by which simvastatin potentiates anti-TB drugs, although an effect on intracellular cholesterol levels cannot be excluded.

#### ***Statin effects on cytokine expression***

In order to gain insight into the anti-TB mechanism of action of statins *in vivo*, the lungs of mice treated with pravastatin adjunctive therapy and those treated with RHZE alone were analyzed by whole-genome microarrays and RT-PCR. Mouse sera were studied by multiplex enzyme-linked immunosorbent assays.

Treatment with pravastatin had a profound effect on the global transcription in mouse lungs ([Table 4](#)).

**Figure 9.** Pravastatin adjunctive therapy for tuberculosis reduces IL-6 in the lungs and serum of mice

Major pathways that were altered after statin treatment included the following: differential regulation of cytokine production in macrophages and T helper cells by IL-17A and IL-17F, the role of JAK family kinases in IL-6-type cytokine signaling pathway, and hematopoiesis from pluripotent stem cells.

Interestingly, global gene expression profiling of the lungs following Mtb infection revealed increased expression of IL-6, and increased IL-6 levels were detected by ELISA in the serum of Mtb-infected mice when compared with uninfected controls. RHZE reduced IL-6 gene expression in mouse lungs and

[figure not shown]
circulating IL-6 (by ELISA) in the serum relative to infected untreated controls ([Figure 9](#)). Pravastatin adjunctive therapy further reduced IL-6 expression in the mouse lungs and serum relative to RHZE controls.

#### Pravastatin adjunctive therapy favorably alters immune cell profiles in mouse lungs

Female BALB/c mice were aerosol-infected with *Mtb* H37Rv and, 6 weeks after infection, were randomized to receive not treatment, human-equivalent doses of the standard first-line regimen (RHZE), or RHZE + pravastatin 90 mg/kg once daily for 28 days. After harvesting the lungs, the intrapulmonary lymphocyte and macrophage populations were measured by FACS. RHZE treatment was found to restore the ratio of alveolar macrophage (AM) to interstitial macrophage (IM) relative to uninfected (naïve) mice. RHZE plus pravastatin 90mg/kg further increased the ratio of AM to IM ([Fig. 10A](#)). Using intracellular cytokine staining, we found that TNF $\alpha$  levels were significantly lower in AM of mice treated with RHZE and pravastatin 90 mg/kg compared to those of control mice or those treated with the control regimen ([Fig. 10B](#)). Similar to the findings with AM, RHZE treatment restored the ratio of CD4 $^{+}$  to CD8 $^{+}$  T cells in mouse lungs and adjunctive therapy with pravastatin 90 mg/kg further increased the ratio of CD4 $^{+}$  to CD8 $^{+}$  T cells ([Fig. 10C](#)).

#### *Effects of statins on anti-TB functions of macrophages*

Treatment of macrophages with 100 nM simvastatin inhibits *Mtb* growth and supplementation with mevalonate was able to partially overcome the anti-TB effect, suggesting that statin treatment was not exerting an off-target effect ([Figure 11A](#)). Moreover, we found that exposure of primary murine macrophages to increasing concentrations of simvastatin resulted in phagosome maturation in a dose-dependent manner. Two parameters of phagosome maturation were tested: proteolytic capacity ([Figure 11B](#)) and acidification ([Figure 11C](#)). Recently, we found that pravastatin 125  $\mu$ M similarly promotes phagosome-lysosome fusion in THP-1 cells (data not shown). The mechanism underlying the statins' antimycobacterial effect and how it links with the observed phagosome/lysosome fusion is being actively investigated. One step is to determine whether the antibacterial activity of the statin can be assigned to a branch of the mevalonate pathway. Our preliminary results rule out a role for farnesylation and type I geranylgeranylation (data not shown). Under current investigation is the role of cholesterol biosynthesis and of the geranylgeranylation type II. The latter is promising because Rab GTPases (which are prenylated by GGT type II) are involved in phagosome maturation and vesicle trafficking. The effects of statins on other immune mediators affecting phagosome/lysosome fusion are also being investigated.

**Figure 11.** Reversal of the anti-Mtb effect of simvastatin in THP-1 cells by addition of mevalonate (A). Proteolysis bead assay (B): Beads were coated with a fluorescently tagged protein (DQ-BSA) and added to cultured macrophages. Substrate hydrolysis in phagocytosed beads results in loss of fluorescence signal (for each dose tested, the increase of signal with time is a function of bead uptake). Acidification bead assay (C): beads were coated with pH-sensitive carboxyfluorescein and added to cultured macrophages. Emission of fluorescence by the phagocytosed beads following excitation at two wavelengths (490nm and 450 nm) varies with phagosomal pH (for each dose tested, ratio decrease with time is a function of bead uptake). Beads only = beads in assay buffer without macrophages.

#### Rationale for conducting the *StAT-TB* clinical trial

Our clinical study to test the adjunctive anti-TB activity of statins is motivated by several lines of investigation. First, several studies have shown that statins have anti-TB properties. We found that statin adjunctive therapy enhances the first-line anti-TB regimen's antimicrobial activity and shortens the time required to achieve cure in a standard mouse model of chronic TB infection ((17, 18) and unpublished data). Recently, we found that 8 weeks of adjunctive therapy with simvastatin or pravastatin significantly reduced lung bacterial burden in the highly clinically relevant C3HeB/FeJ mouse model of chronic TB, which develops human-like, necrotic TB lung granulomas(19-21). Parihar et al. showed that peripheral blood mononuclear cells and monocyte-derived macrophages from patients with familial hypercholesterolemia receiving statin therapy were more effective in controlling Mtb growth compared with those of healthy donors, through induction of autophagy and promotion of phagosome maturation (22). In addition, statins are synergistic with the key sterilizing drug, rifampin (23). Recent data from observational studies suggest that statin use among patients with type 2 diabetes mellitus may reduce the frequency of incident TB cases (25, 26). Second, statins have immune-modulatory properties and statin use improves mortality in patients with sepsis (44, 45) or with community-acquired pneumonia (51). Several studies have shown that statins reduce lung inflammation in the mouse model of chronic TB (22) (and unpublished data). Our data suggest that these effects may be mediated by modulation of lung cytokine expression, including reduction of levels of IL-6 and TNF $\alpha$ , and an increase in the ratio of CD4 $^+$ /CD8 $^+$  T cells in the lungs of Mtb-infected mice. Third, statins are among the most widely used drugs worldwide, and their safety profile is well documented and highly favorable (27). Fourth, statins and antiretroviral drugs can be co-administered (with drug and dose selection) (28), so patients with HIV infection on antiretroviral treatment (ART) may also benefit. Fifth, statins are attractive adjunctive agents for TB treatment due to the widespread availability of less costly generics. This is particularly important for TB, which is endemic primarily in resource-limited settings.

Of 8 statins tested, pravastatin was selected for testing in the current study based on its favorable CC50/EC50 values and demonstration of adjunctive activity against chronic TB in the standard mouse model. Specifically, pravastatin demonstrated the least toxicity of all statins in our assays (CC50> 1.25 mM and > 10 mM in THP-1 and Vero cells, respectively) and was one of 3 statins for which an EC50

could be obtained within the tested range in THP-1 cells (7.8  $\mu$ M), yielding a highly favorable CC50/EC50 >160.3. Importantly, pravastatin showed dose-dependent activity against chronic TB in the standard mouse model, and improved the percent surface area of lung involved by inflammation. Adjunctive therapy with pravastatin 50 mg/kg, which yields human-like drug exposures following an 80-mg dose, significantly reduced the lung bacillary burden in a clinically relevant mouse model of necrotic TB granulomas (C3Heb/FeJ mice) relative to controls receiving the first-line regimen alone. Although simvastatin also showed a highly favorable CC50/EC50 ration in macrophages and adjunctive activity in both mouse models of chronic TB, several factors dampened our enthusiasm for this agent relative to pravastatin. Based on our PK data, simvastatin is almost entirely converted to its acid metabolite in mice, whereas in humans metabolism to simvastatin acid is ~1:1. Since we do not know if the parent drug or acid metabolite is responsible for the anti-TB effect, it is possible that the mouse data overestimate the adjunctive activity of simvastatin. Perhaps more importantly, peak concentrations of both simvastatin and simvastatin acid are greatly reduced (by 90%) by rifampin (69). On the other hand, pravastatin exposures are reduced by only 30-50% during co-administration with rifampin (70). Our PK data suggest that drug clearance and exposures differ markedly between mice and humans. Given that we observed a dose-responsive anti-TB effect with pravastatin adjunctive therapy in mice and the known drug interactions between pravastatin and rifampin in humans, we will study the safety/tolerability and PK of the highest clinically recommended dose of pravastatin (80 mg daily) in this clinical trial. Due to the anticipated ~50% reduction in 24-hour pravastatin exposures when the drug is co-administered with rifampin, dose escalation (if tolerated) will continue up to 160 mg daily. The anti-TB effect of adjunctive statin therapy observed in mice was accompanied by a reduction in serum IL-6 ([Figure 9](#)) to levels seen in uninfected mice. If safety, tolerability, and PK of pravastatin adjunctive therapy are deemed acceptable following completion of this study, we will proceed to a larger follow-up study in which we will also explore the potential treatment-shortening and immunomodulatory effects of pravastatin adjunctive therapy for TB.

#### **4. Study Procedures**

##### ***Protocol Registration***

Prior to implementation of this protocol, and any subsequent full version amendments, each site must have the protocol and the protocol informed consent form(s) approved, as appropriate, by their local institutional review board (IRB)/ethics committee (EC) and any other applicable regulatory entity (RE). Upon receiving final approval, sites will submit all required protocol registration documents to the DAIDS Protocol Registration Office (DAIDS PRO) at the Regulatory Support Center (RSC). The DAIDS PRO will review the submitted protocol registration packet to ensure that all of the required documents have been received.

Site-specific informed consent forms (ICFs) *WILL* be reviewed and approved by the DAIDS PRO and sites will receive an Initial Registration Notification from the DAIDS PRO that indicates successful completion of the protocol registration process. A copy of the Initial Registration Notification should be retained in the site's regulatory files.

Upon receiving final IRB/EC and any other applicable RE approval(s) for an amendment), sites should implement the amendment immediately. Sites are required to submit an amendment registration packet to the DAIDS PRO at the RSC. Site-specific ICF(s) *WILL NOT* be reviewed and approved by the DAIDS PRO and sites will receive an Amendment Registration Notification from the DAIDS PRO that approves the site specific ICFs and indicates successful completion of the amendment protocol registration process. A copy of the final amendment Registration Notification issued by the DAIDS PRO should be retained in the site's regulatory files.

##### ***Screening***

Participants with a presumptive diagnosis of sputum GeneXpert positive pulmonary TB will be invited to participate. Because culture confirmation is rarely available when TB treatment is initiated, patients will be recruited based on having a sputum specimen that is positive for TB by GeneXpert MTB/RIF.

Informed written consent, using IRB-approved consent forms, will be obtained by trained study personnel prior to performing any study-specific procedures. Informed consent is a process that will be initiated prior to the individual's agreeing to participate in the study and will continue throughout the individual's study participation.

The following will be performed after obtaining written informed consent:

- Eligibility criteria will be confirmed
- All participants will undergo HIV testing and counseling regardless of whether they have had a previous HIV test or not. HIV testing will be carried out with two rapid tests (the second test will be to confirm the result of the first); only one test need be carried out if the participant is known to have HIV, the single test will be confirmatory. Should there be a discrepancy between the two rapid tests, blood will be sent to the laboratory for enzyme-linked immunosorbent assay ELISA and Western Blot test in order to confirm the diagnosis.
- For HIV-positive participants, a CD4 count should be performed unless written results are available from a test done within the preceding 3 months or less.
- Participants will be asked questions related to demographics, current and past medical history, concomitant medications, alcohol and drug use and TB symptoms.
- Participants will have heart rate, blood pressure, respiratory rate, temperature and weight measured.
- An expectorated sputum sample will be obtained for GeneXpert MTB/RIF (as per inclusion criterion d), smear, culture, and drug susceptibility testing at the study laboratory (or documentation of results).
- Blood will be drawn for liver function tests (AST, ALT, total bilirubin), Hepatitis B and C serology, CK, serum creatinine, CBC (WBC, hemoglobin, and platelets).
- A posterior anterior chest radiograph will also be taken, unless a posterior anterior chest radiograph done within the previous 14 days or less is available for review.
- Urine will be collected for pregnancy testing if a woman is of child-bearing potential.
- Complete physical exam and vital signs
- 
- Targeted symptom assessment

The Screening evaluation process itself may occur over a few days with more than one visit, however, all Screening evaluations will be obtained within 3 days of study entry.

***Day 1 (Baseline)***

- Treatment Assignment
- DOT of pravastatin
- Adverse event assessment
- Chemistry (Comprehensive metabolic panel: total cholesterol, LDL, , C-reactive protein, uric acid)
- Intensive PK for pravastatin
- Lung inflammation assessment (PFT, St. George's respiratory questionnaire, 6-minute walk test); +/- 3 days.
- Targeted symptom assessment
- Sputum

***Day 2***

- Intensive PK for pravastatin
- DOT of pravastatin and TB treatment
- Adverse event assessment

***Days 3-6***

- DOT
- Adverse event assessment

***Day 7 (Week 1)***

- Targeted symptom assessment
- Concomitant medications
- DOT
- Adverse event assessment
- Sputum
- Liver function tests
- Chemistry (Comprehensive metabolic panel:, total cholesterol, LDL, , C-reactive protein, uric acid)
- CK, serum creatinine

***Days 8-14***

- DOT
- Adverse event assessment

***Day 15 (Week 2)***

- Targeted symptom assessment
- Concomitant medications
- DOT
- Adverse event assessment
- Sputum
- Liver function tests
- Chemistry (Comprehensive metabolic panel:, total cholesterol, LDL, , C-reactive protein, uric acid)

- Urine pregnancy test
- Intensive PK for pravastatin
- Lung inflammation assessment (PFT, St. George's respiratory questionnaire, 6-minute walk test); +/- 3 days.
- CK, serum creatinine

***Day 21***

- Chemistry,(Comprehensive metabolic panel: total cholesterol, LDL, C-reactive protein, uric acid)
- Liver function tests
- Targeted symptom assessment
- Adverse event assessment
- CK, serum creatinine

***Day 30 (Month 1)***

- Targeted symptom assessment
- Liver function tests
- Chemistry (Comprehensive metabolic panel: total cholesterol, LDL, C-reactive protein, uric acid)
- Lung inflammation assessment (PFT, St. George's respiratory questionnaire, 6-minute walk test); +/- 3 days
- Urine pregnancy test
- Adverse event assessment
- CK, serum creatinine
- 

***Unscheduled visit***

- Exam and vital signs
- Targeted symptom assessment
- Adverse event assessment
- Concomitant medications
- Liver function tests
- Chemistry

***TB treatment continuation***

All study participants will be referred appropriately to continue standard TB treatment at study completion.

***Targeted symptom assessment***

Participants will be asked whether they have experienced any of the following since the last study visit: fevers, sweats, cough, rash, itching, jaundice, nausea, vomiting, diarrhea, loss of appetite, vision problems, numbness/tingling of extremities, headache, joint pain, eye pain. In addition, patients will be asked whether they have had other symptoms (not listed above); if yes, then these symptoms will be recorded and graded. In addition, targeted diagnostic evaluations may be indicated to determine the underlying cause of symptoms and their association with study drug use.

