### ***Clinical Management of Adverse Events***

#### Liver toxicity

Study treatment will be permanently discontinued if any of the following criteria are met:

- ALT > 5x the upper limit of normal (ULN) without symptoms
- ALT > 3x ULN with signs or symptoms suggestive of clinical hepatitis including one or more of the following: nausea, vomiting, abdominal pain, dark colored urine or clay colored stools, unexplained fever, jaundice, liver tenderness, or hepatomegaly
- ALT > 3x ULN and Total Bilirubin  $\geq$  2x ULN

If a patient develops hepatic toxicity meeting the above stopping criteria, the following evaluation will be undertaken: assessment for history of injection or non-injection drug use, alcohol ingestion, use of other hepatotoxic drugs, and performance of serologic tests for viral hepatitis (IgM antibody for Hepatitis A, Hepatitis B surface antigen, IgM antibody to Hepatitis B core antigen, antibody to Hepatitis C). In addition, an AST and INR should also be checked, if not already done.

Participants will be followed until resolution (return to baseline) or stabilization of the ALT elevation.

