### ***Decision-making algorithm for pravastatin safety/PK study:***

Scenario/Pravastatin Dose	Safe/tolerable?	<math>AUC_{0-24}</math> reduction	Decision
1 40 mg daily	Y	=	Increase dose to prava 80 mg and enroll additional participants
2 40 mg daily	N	=	Enroll 5 additional participants (10 total) and discontinue study

3 80 mg daily	N	=	Discontinue study
4 80 mg daily	Y	< 40%	Discontinue study
5 80 mg daily	Y	≥ 40%	Increase dose to prava 120 mg and enroll additional participants
6 120 mg daily	N	=	Discontinue study
7 120 mg daily	Y	<40%	Discontinue study
8 120 mg daily	Y	≥ 40%	Increase dose to prava 160 mg and enroll additional participants
9 160 mg daily	N	=	Discontinue study
10 160 mg daily	Y	=	Study complete

Safety/tolerability: Y= Yes; <3 participants with  $\geq$  one grade 3 (or higher) event of musculoskeletal symptoms, creatine kinase elevation, or liver function test elevation attributed to study drug (probable or definite)

N= No; For Arm 1 (pravastatin 40 mg daily):  $\geq$  1 participant with  $\geq$  one grade 3 (or higher) event of musculoskeletal symptoms, creatine kinase elevation, or liver function test elevation attributed to study statin medication (probable or definite).

For Arms 2, 3, and 4:  $\geq$  3 participants with  $\geq$  one grade 3 (or higher) event of musculoskeletal symptoms, creatine kinase elevation, or liver function test elevation attributed to study statin medication (probable or definite)

$AUC_{0-24}$ = Area-under-the-plasma-concentration-time curve for 24-hour exposure

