#### ***Decision-making algorithm for initiating new dosing cohorts***

The study will be monitored by a DSMB, which will review the safety data for each cohort and will give approval before initiation of each possible dose escalation. Specifically, study drug dose will not be escalated and the study if any three participants develop grade 3 or higher musculoskeletal/CK-related adverse events (AEs), LFT-related AEs ( $> 5 \times UNL$  without symptoms, but  $> 3 \times UNL$  with symptoms or bilirubin  $> 2 \times ULN$ ) or any type of grade 4 event regardless of causal attribution. Study drug dosage will be escalated only if the dose is deemed safe/tolerable based on the above rules and the mean pravastatin AUC is reduced by  $\geq 40\%$  relative to the pre-Rifafour value. Study participants in whom the study drug has been discontinued will remain in the study until the final clinical visit and laboratory evaluation. In the event of study product discontinuation, management of the standard-of-care TB drugs will revert to the site clinician as per national guidelines.

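### The targeted symptom list does not ask about muscle pain, tenderness or weakness, although grade 3 or higher musculoskeletal events count towards the dose-escalation decision

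*Combined protocol and SAP*

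**What the plan says.** Section 4, Targeted symptom assessment, lists the symptoms that participants are asked about: "fevers, sweats, cough, rash, itching, jaundice, nausea, vomiting, diarrhea, loss of appetite, vision problems, numbness/tingling of extremities, headache, joint pain, eye pain". The last four, "numbness/tingling of extremities, headache, joint pain, eye pain", cover joints and eyes but not muscles. It then adds an open prompt: "patients will be asked whether they have had other symptoms (not listed above); if yes, then these symptoms will be recorded and graded". The visit lists and Appendix 1 place this assessment at Screening, Days 1, 7, 15, 21 and 30, and unscheduled visits.

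Section 18 uses muscle symptoms in the dose decision twice. The decision table for the safety/PK study counts any participant with a grade 3 or higher "event of musculoskeletal symptoms, creatine kinase elevation, or liver function test elevation attributed to study drug", where attribution must be probable or definite. The section on initiating new dosing cohorts counts "grade 3 or higher musculoskeletal/CK-related adverse events (AEs), LFT-related AEs".

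Section 5, Myalgias and Myopathy, defines myopathy as muscle aching, soreness, tenderness or weakness with CK above 10 times the upper limit of normal (ULN). Section 5, Liver toxicity, has an ALT stop above 3 times ULN that applies when there are "signs or symptoms suggestive of clinical hepatitis including one or more of the following: nausea, vomiting, abdominal pain, dark colored urine or clay colored stools", with further items after these.

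**The concern.** A prompted list finds more than an open question does, and the choice of prompts should follow the events that drive the decision. This list fits the TB drugs better than the study drug. By the protocol's own drug descriptions, joint pain matches pyrazinamide, vision problems match ethambutol, and numbness or tingling matches isoniazid. Muscle problems are the pravastatin risk named in section 13 under drug interactions, and they have no prompt.

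The trial's primary outcome is safety and tolerability, and escalation depends on small counts. If a qualifying muscle event is not elicited, the cohort looks safer than it was and the next dose may be opened on an incomplete count.

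The liver rule raises a related but smaller question, because some of its qualifying symptoms are also absent from the list.

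**Working it through.** No figure in the plan needs reproducing here. The check is a comparison of texts, followed by a short argument on direction.

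**1. Symptoms used by the rules against the 15 listed items**

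| Symptom used elsewhere in the protocol | On the targeted list? |
|---|---|
| Muscle aching, soreness, tenderness, weakness (Myalgias and Myopathy) | 0 of 4 |
| Nausea, vomiting, fever, jaundice (Liver toxicity) | 4 of 4 |
| Abdominal pain, dark urine, clay-colored stools (Liver toxicity) | 0 of 3 |
| Liver tenderness, hepatomegaly (Liver toxicity) | Not listed; largely examination findings |

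The only musculoskeletal item on the list is joint pain.

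**2. How each event type in the decision table is found**

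- CK elevation: CK is drawn at Screening and on Days 7, 15, 21 and 30.
- Liver test elevation: AST, ALT and bilirubin are drawn at the same visits and at unscheduled visits.
- Musculoskeletal symptoms: these count on their own, without CK elevation. No scheduled test detects them.

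**3. Other routes for muscle symptoms**

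- The open prompt in the targeted assessment.
- A daily adverse event assessment by a trained team member (Safety Evaluation; Appendix 1). No symptom list is given. It is justified by directly observed treatment, but Administration of study drug lets a trained family member, employer or lay supervisor observe doses.
- A standardised checklist used at each visit (section 9). Its items are not stated, so it cannot be assumed either to include or to omit muscle symptoms.
- A 24-hour telephone number, and an adverse event check after any missed visit (section 9).

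The unscheduled visit lists the symptom assessment, liver tests and chemistry but not CK. Grade 3 or higher myalgia prompts a CK evaluation under Myalgias and Myopathy. If it is neither asked about nor volunteered, nothing in that visit list prompts one.

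**4. Direction of the effect**

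Let T be the number of participants in a cohort with a qualifying event, and M the number among them whose only qualifying event is a muscle symptom that was missed. The observed count is O = T − M, so O ≤ T always. With a failing count of k, the decision changes only if T ≥ k and T − M < k. The change is always from not safe to safe.

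The protocol does not give a single k. For Arm 1 the decision table's No definition gives k = 1, while its Yes definition, which names no arm, accepts fewer than 3. For Arms 2 to 4 the table gives k = 3. Data Analysis accepts up to 3 participants with grade 3 or higher events, which implies k = 4, and separately requires that nobody discontinue for a pravastatin-related reaction.

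**5. Why no size is given**

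The size depends on the rate of grade 3 or higher muscle events without CK elevation, and on the share that the existing routes would miss. The documents give neither. The nearest figure, in section 13 under Tolerability, is CK above 10 times ULN in 4 of 464 patients on 80 mg (4/464 = 0.9%) against 0 of 115 on 40 mg. That concerns CK alone.

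**The case against.** The strongest objection is that only grade 3 or higher events count. The protocol describes grade 3 myalgia as muscle pain that stops a person's normal activities. With a daily assessment and an open question, such an event is far less likely to be missed than a mild ache, and mild aches do not enter the rule. This stands, and it is why the effect is probably modest.

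Myopathy as defined also needs CK above 10 times ULN. CK elevation of grade 3 or higher leads to statin discontinuation whatever the symptoms, so any delay in recognising myopathy is confined to the time between scheduled draws. This stands too, but it does not cover muscle symptoms without CK elevation.

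Four stronger readings are tempting and are not supported:

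- *That muscle symptoms go uncollected.* The routes in step 3 of the working exist; what is missing is a stated prompt.
- *That the key safety component is the only one not asked about.* Joint pain is a musculoskeletal item and is asked about. The other two components are laboratory values, which are measured rather than asked about.
- *That the symptom-dependent ALT stop cannot work.* One qualifying feature is enough and four are already on the list. ALT above 5 times ULN, and ALT above 3 times with bilirubin at least 2 times ULN, need no symptoms. The gap concerns only a participant with ALT between 3 and 5 times ULN, bilirubin below 2 times ULN, and an unlisted symptom as the sole qualifying feature.
- *That the loss can be expressed as a fall in the chance of stopping escalation.* Reducing all events by a common fraction would be wrong, because CK and liver events are found by scheduled blood tests. Any starting event rate would be invented.

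**Conclusion.** The point holds for muscle symptoms. The list leaves out all four muscle complaints by which the protocol defines myopathy, while both statements of the escalation rule count musculoskeletal events. The direction is certain: a missed event can only favour a finding of safety. The size cannot be calculated from the documents and is probably modest.

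This rests on two assumptions: that the checklist in section 9 does not already prompt for muscle symptoms, and that prompting elicits some events that open questions would not. If that checklist does contain the items, the remaining task is to make the two lists agree.

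The liver symptoms are a minor alignment and would not justify a change on their own.

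**What to change.** Add muscle pain or aching, tenderness and weakness, as already named under Myalgias and Myopathy, to the targeted symptom list at every visit where it is used: Screening, Days 1, 7, 15, 21 and 30, and unscheduled visits. Screening and Day 1 matter because Rifafour starts on Day 2. The decision table counts only events attributed to pravastatin as probable or definite, and section 13 notes that rifampin can itself cause myalgia, though uncommonly. A pre-Rifafour record gives attribution a baseline.

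As a minor alignment, add abdominal pain and dark urine or clay-colored stools from the Liver toxicity list. State the items of the section 9 checklist, or say that it is the same list.

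The cost is a few items on an existing form and slightly more low-grade symptoms recorded. Under section 5, Reporting, a mild ache would not by itself require an Adverse Event Report Form. No dose, threshold or stopping rule changes.
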